#### For Cohort 1 and Cohort 2:

- If eligibility is determined by pre-existing test results or pre-screening by a local laboratory, then tumor tissue sample must be sent to the central laboratory for confirmation of the FGFR genetic alteration. The tumor tissue sent for confirmatory testing should be from the same biopsy sample that was used to determine eligibility.
- If an archival tissue sample is not available, a new tumor biopsy must be obtained before BGJ398 treatment. Refer to the Laboratory Manual for additional details on the amount of tumor tissue required for testing by the central laboratory.
- If written documentation of FGFR genetic alteration in tumor tissue is available from the central laboratory, an additional tumor sample does not need to be submitted for central molecular testing.

For Cohort 3, written documentation of the FGFR2 gene fusion from a clinically-validated test on a sample (tumor tissue or cell-free DNA from blood) collected after treatment with the prior FGFR inhibitor is highly recommended. If written documentation is not available, a tumor sample collected after treatment with the prior FGFR inhibitor may be submitted to the central laboratory but is not required for enrollment.

QED Therapeutics designated lab(s) will be used for processing of all tumor samples collected. The central laboratory will provide kits to collect and ship these samples to QED Therapeutics designated lab(s) for analysis. Details on the collections, shipment of samples are provided to investigators in the laboratory manual.

While the goal of the biomarker assessments is to provide supportive data for the clinical study, there may be circumstances when a decision is made to stop a collection, or not perform or discontinue an analysis due to either practical or strategic reasons (eg, inadequate sample number, issues related to the quality of the sample or issues related to

the assay that preclude analysis, impossibility to perform correlative analyses, etc.). Therefore, depending on the results obtained during the study, sample collection analysis may be omitted at the discretion of QED Therapeutics.

Table 12: Biomarker sample collection plan

Sample Type	Tissue Amount	Visit	Time point
Archival tumor tissue and corresponding pathology report (to determine patient's FGFR status) a OR Newly obtained tumor sample	A tumor block is preferred or a minimum of 15-20 slides	Molecular pre-screening for central testing Requires Molecular prescreening ICF	Any time prior to starting study-specific screening procedure (patient must have required genetic alteration in order to start screening)
Archival tumor tissue and a corresponding pathology report b OR Newly obtained tumor sample if archival sample is not available (highly recommended for Cohort 3).	A tumor block is preferred or a minimum of 15-20 slides.	Screening	Day -28 up to day -1
Optional-Newly obtained tumor sample (if feasible)	Tumor tissue (formalin fixed paraffin embedded) 11-20 unstained slides	For patients who have had a response upon disease progression	Upon disease progression
Blood (plasma) for circulating tumor DNA (cell free DNA) assessment b	~ 10.0mL	Screening/ baseline, C2D1, day 1 of every odd numbered cycle and at progression/ end of treatment (should be taken prior to biopsy procedure)	Circulating tumor DNA assessment

a Only needed if pre-screening is done by the QED Therapeutics designated lab

#### 7.2.4.1 Archived tumor samples

Collection of an archival tumor sample (tissue blocks or 11-20 unstained slides) is mandatory and will be collected from all patients at screening if a sample was not submitted to the central laboratory for FGFR molecular prescreening. A corresponding pathology report should be included along with the archival sample. If an archival tumor sample is not available, a newly obtained tumor sample should be obtained and provided as a formalin-fixed, paraffin-embedded block. Archival or newly obtained tumor samples will be used to explore mechanisms of resistance to cancer treatment through analysis of next generation DNA sequencing data from tumor samples at baseline and after the

Only if not submitted to the central laboratory for FGFR molecular pre-screening

development of disease progression (whenever available). Additional archival sample may be requested if the original sample sent is of insufficient quantity or quality to complete the planned analysis.

Confidential

The sample collection must be captured on the appropriate eCRF and requisition page(s). Detailed instructions for the collection, handling, labeling, and shipment of samples are outlined in the CRO Laboratory Manuals.

#### 7.2.4.2 Newly obtained tumor samples

A newly obtained tumor sample should be collected at progression (end of treatment) for patients if safe and feasible, as it will provide a unique opportunity to investigate the potential mechanisms of resistance to BGJ398. This will be performed using a combination of genomic, transcriptomic and proteomic technology, which may include profiling of mutation, amplification and/or modification in DNA, RNA, or protein levels in tumor tissue.

The sample collection must be captured on the appropriate eCRF and requisition page(s). Detailed instructions for the collection, handling, labeling, and shipment of samples are outlined in the CRO Laboratory Manuals.

#### 7.2.4.3 Exploratory biomarkers- cell free DNA assessment

Blood (approximately 10 ml) will be collected at screening, Cycle 2 Day 1, day 1 of every odd numbered cycle at the time of response assessment scans, and at the time of disease progression (EOT). These samples will be used for analysis of cell-free DNA to explore whether genetic alterations found in tumor samples may also be observed in blood, and if any alterations found are predictive of response and/or associated with development of resistance.

Detailed instructions for the collection, handling and shipment of samples are outlined in the [CBGJ398X2204 Laboratory Manual].

## 7.2.4.4 Optional additional exploratory biomarker assessments using the remaining biomarker samples

Patients will have the opportunity to consent to use of their remaining samples (tissue, tumor DNA, or blood) for additional research related to BGJ398, cancer or other study treatments. This may also include research to help develop ways to detect, monitor or treat cancer. A decision to perform such exploratory biomarker research studies would be based on outcome data or from new scientific findings related to the drug class or disease, as well as reagent and assay availability.

Remaining tissue and cell free DNA samples may be subjected to genetic testing (DNA, RNA, protein) to profile genetic alterations in these samples. The investigators and patients will not receive the results from future research. The biological samples will be coded with a unique number that links the samples to the study patient in the study database as part of de-identification of the samples.

The samples may be stored under QED Therapeutics' control or by its authorized agents. The samples will be stored up to 15 years. The period of time that data derived from future research may be used is not specified and these data may be used indefinitely. The data may be shared with Health Authorities worldwide, at medical meetings, or in medical publications. Participation is optional for patients to have their tissue and blood used in future research. Patients can request that QED Therapeutics not use their stored samples for future research, to the extent that they have not already used the sample, and to the extent that they are able to locate the sample after it has been de-identified. Patients who fail prescreening or fail screening will not have their samples stored for future research.

#### 8 SAFETY MONITORING AND REPORTING

#### 8.1 Adverse events

## 8.1.1 Definition and reporting

An adverse event is defined as the appearance of (or worsening of any pre-existing) undesirable sign(s), symptom(s), or medical condition(s) that occur after patient's signed informed consent has been obtained. (Adverse events that occur before a patient signs the informed consent are recorded on the Medical History/Current Medical Conditions eCRF.) Adverse events that occur after informed consent is signed and prior to initiation of study treatment will only be captured if they meet the definition of serious adverse events and are reported to be causally related with study procedures (eg, an invasive procedure such as biopsy). All other adverse events occurring after informed consent is signed prior to initiation of study treatment should be recorded as medical history. Adverse event monitoring and recording should be continued for at least 30 days following the last dose of study treatment.

For patients who sign the molecular pre-screening ICF, AEs which occur after signature of this consent will only be captured if they meet the definition of serious as outlined in Section 8.2 and are reported to be causally related with study procedures (e.g. an invasive procedure such as biopsy).

Patients with known FGFR2 gene fusions or other FGFR genetic alteration status will only sign the main study ICF and AE collection for these patients will start from the time of signing the main ICF.

Adverse events (including lab abnormalities that constitute AEs) should be described using a diagnosis whenever possible, rather than individual underlying signs and symptoms. When a clear diagnosis cannot be identified, each sign or symptom should be reported as a separate Adverse Event.

Adverse events will be assessed according to the Common Terminology Criteria for Adverse Events (CTCAE) version 4.03. If CTCAE grading does not exist for an adverse event, the severity of mild, moderate, severe, and life-threatening, corresponding to Grades 1 - 4, will be used. CTCAE Grade 5 (death) will not be used in this study. Rather,

if the patient dies while on study, the death will be captured on the End of Treatment disposition eCRF. If the patient dies while in follow-up, the death will be captured on the End of Study disposition eCRF and if the patient dies post-follow-up and is being followed for survival, their death will be captured on the Survival Follow-up eCRF. The occurrence of adverse events should be sought by non-directive questioning of the patient during the screening process after signing informed consent and at each visit during the study. Adverse events also may be detected when they are volunteered by the patient during the screening process or between visits, or through physical examination, laboratory test, or other assessments. As far as possible, each adverse event should be evaluated to determine:

- 1. The severity grade (CTCAE Grade 1-4)
- 2. Its duration (start and end dates)
- 3. Its relationship to study drug (reasonable possibility that AE is related: No, Yes)
- 4. Action taken with respect to study treatment (none, dose adjusted, temporarily interrupted, permanently discontinued, unknown, not applicable)
- 5. Whether medication or therapy was given (no concomitant medication/non-drug therapy given, concomitant medication/non-drug therapy given)
- 6. Outcome (not recovered/not resolved, recovered/resolved, recovering/resolving, recovered/resolved with sequelae, fatal, unknown)
- 7. Whether it is serious, where a Serious Adverse Event (SAE) is defined as in Section 8.2.1.

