#### 7.1.2.2 Information to be collected for screen failures

Patients who signed a molecular pre-screening ICF but are considered as ineligible after molecular screening, as well as patients who are found not eligible after signing the informed consent form to participate in the treatment phase of the study, will be considered as screening failures, and data will be handled in the same manner. The reason for not being started on study treatment will be entered on the screening phase disposition page. For all screening failure patients, demography, inclusion/exclusion and informed consent information along with the reason for screen failure will be collected. No other data will be entered in the database for patients who are screen failures, unless the patient experienced a Serious Adverse Event during the screening phase (see Section 8 for SAE reporting details). For molecular prescreening failures, only SAEs possibly related to a study procedure will be reported.

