## 8.2.2 Reporting

For patients whose FGFR2 gene fusions or other FGFR genetic alteration status is unknown, SAE collection will start upon signing the molecular pre-screening ICF. SAEs will only be reported if the event is suspected to be causally related to a study procedure as assessed by the investigator (e.g. an invasive procedure such as biopsy). SAEs will be followed until resolution or until clinically relevant improvement or stabilization. If the main ICF is not signed (molecular screen failure), SAE collection ends 30 days after the last study related procedure. If the main ICF is signed, SAE collection is as below.

Patients with known FGFR2 gene fusions or translocations/other FGFR genetic alteration status who do not sign the molecular pre-screening ICF, SAE collection starts at the time of signing main study informed consent regardless of whether the patient is found to be a screen failure.

To ensure patient safety, every SAE, **regardless of suspected causality**, occurring after the patient has provided informed consent and until at least 30 days after the patient has stopped study treatment must be reported to Covance Safety (email: [contact]; [contact]) within 24 hours of learning of its occurrence. Any SAEs experienced after this 30 days period should only be reported to Covance Safety if the investigator suspects a causal relationship to the study treatment. Any additional information for the SAE including recurrent episodes, complications, or progression of the initial SAE must be reported as follow-up to the original episode within 24 hours of the investigator receiving the follow-up information. An SAE

occurring at a different time interval or otherwise considered completely unrelated to a previously reported one should be reported separately as a new event.

Confidential

Information about all SAEs is collected and recorded on the Serious Adverse Event Report Form; all applicable sections of the form must be completed in order to provide a clinically thorough report. The investigator must assess and record the relationship of each SAE to each specific study treatment (if there is more than one study treatment), complete the SAE Report Form in English, and submit the completed form within 24 hours to Covance Safety (email: [contact]; [contact]). Detailed instructions regarding the submission process and requirements for signatures are to be found in the investigator folder provided to each site.

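### Between main consent and first dose, Protocol 8.1.1 and 8.2.2 give opposite instructions for SAEs not related to a study procedure

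*Protocol*

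**What the plan says.** Protocol 8.1.1 (Definition and reporting) sets the rule for the interval from signed consent to first dose. Adverse events in that interval "will only be captured if they meet the definition of serious adverse events and are reported to be causally related with study procedures". It then disposes of the remainder: "All other adverse events occurring after informed consent is signed prior to initiation of study treatment should be recorded as medical history". No exception is made for an event that is serious but not linked to a procedure. A separate paragraph of 8.1.1 applies the same serious-and-procedure-related filter to patients who sign the molecular pre-screening consent.

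Protocol 8.2.2 (Reporting) sets the SAE rule. It applies "regardless of suspected causality", so no judgement about cause can take an event out of it. Its window is any SAE "occurring after the patient has provided informed consent and until at least 30 days after the patient has stopped study treatment", and the safety group has to receive the report within 24 hours of the site becoming aware. For patients whose FGFR status is already known and who skip the pre-screening consent, "SAE collection starts at the time of signing main study informed consent regardless of whether the patient is found to be a screen failure". For patients who have signed only the pre-screening consent, "SAEs will only be reported if the event is suspected to be causally related to a study procedure as assessed by the investigator"; once they sign the main consent, the general rule takes over.

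Protocol 7.1.2.2 limits the data entered for screen failures "unless the patient experienced a Serious Adverse Event during the screening phase". It adds a causality condition only for molecular pre-screening failures.

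**The concern.** A site needs a single answer to a simple question: what to do with an SAE that occurs after the main consent, before the first capsule, and has nothing to do with a study procedure. Section 8.1.1 and section 8.2.2 answer it differently.

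Two things are at stake. The first is expedited reporting. Protocol 8.6 says there is no data monitoring committee and relies on prompt review of safety data by the sites and the sponsor, so that review depends on sites submitting SAEs on the same basis. The second is the safety listings. Protocol 10.5.2.2 promises listings that include pre-treatment safety data, and SAP 2.7.2.1.2 plans a listing of all serious adverse events, while stating that adverse event listings draw on the AE page of the case report form. An event filed as medical history is not on that page.

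**Working it through.** No arithmetic applies. The check is to take each kind of pre-dose SAE and read off what each section requires.

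1. **Only the molecular pre-screening consent signed; SAE not procedure-related.** 8.1.1: not captured. 8.2.2: not reported. 7.1.2.2: not reported for pre-screening failures. The three agree.
2. **Main consent signed, before first dose; SAE procedure-related.** 8.1.1: captured. 8.2.2: reported within 24 hours. They agree.
3. **Main consent signed, before first dose; SAE not procedure-related.** 8.1.1: recorded as medical history. 8.2.2: reported within 24 hours. 7.1.2.2: entered if the patient becomes a screen failure. 8.1.1 conflicts with the other two.
4. **After first dose.** The 8.1.1 restriction no longer applies. No conflict.

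The conflict is therefore confined to case 3.

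Two readings might remove it, and neither does.

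- *The restriction in 8.1.1 was meant only for the pre-screening consent.* The pre-screening consent has its own paragraph in 8.1.1, with the same filter. The first paragraph would be redundant unless it also covered the main consent.
- *Captured refers to the case report form and reported refers to the safety form.* Neither section states this distinction. For the pre-screening consent, 8.1.1 uses one verb and 8.2.2 the other for the same criterion, which suggests they are interchangeable.

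The reach into the analysis is limited. SAP 2.1.1.5 defines the pre-treatment period as running from first consent to the day before first dose. SAP 2.7.2.1.2 counts an event as treatment-emergent only if it starts on or after the first day of treatment. A case 3 event can therefore appear in listings but not in any treatment-emergent summary, so those summaries are the same whichever rule a site follows.

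**The case against.** The strongest reply is that 8.1.1 points elsewhere for SAEs: a line within that section says they have their own reporting requirements and refers to 8.2. Section 8.2.2 is the specific rule and stresses that causality does not matter, and 7.1.2.2 leans the same way. The sections also name different forms: 8.1.1 mentions the medical history page and 8.2.2 the SAE report form. A site could file the event as medical history and still send the SAE form. Protocol 9.2 requires monitors to verify SAE documentation in full, which may catch omissions.

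Much of this stands. It means that loss of these SAEs is a risk and not a certainty. A reader might infer that the two sections cannot both be obeyed in any sense, or that such events will never reach central safety review; the documents support neither statement. But the pointer to 8.2 does not exempt SAEs from the medical-history instruction. A site that used both forms could leave the event in the safety records but outside the AE page from which the listings are drawn. Monitors verifying SAE documentation would also be working from two different rules.

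A reader might also infer that the problem covers the whole period from any consent, for all of the approximately 160 planned patients, over 21 or 28 days. That does not follow:

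- The pre-screening rules are consistent.
- The 21-day and 28-day figures are windows for assessments and imaging, not the time from consent to dose. Protocol 7.1.2 allows procedures from routine work-up to precede consent.
- Many Cohort 1 patients were dosed under earlier protocol versions. The amendment summaries show that 8.1.1 was edited in Amendments 4 and 5, and the text that applied to those patients is not available.

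**Conclusion.** The inconsistency is real and narrow. For SAEs not related to a study procedure, between the main study consent and first dose, 8.1.1 directs the site to medical history while 8.2.2 directs it to a 24-hour report, with 7.1.2.2 on the side of 8.2.2. Sites that follow 8.1.1 may not report these events. Expedited reporting and the listing of all SAEs may then be incomplete, and unevenly so across sites.

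The size cannot be given: neither the number of such events nor the number of patients exposed to the conflicting text is in the documents. Treatment-emergent summaries are unaffected. This is a minor wording defect with a safety-reporting consequence, and it is worth correcting because the correction is cheap. The conclusion assumes that the site has no further instruction, outside the protocol and SAP, that settles which section prevails.

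**What to change.** Reconcile 8.1.1 with 8.2.2 and 7.1.2.2 so that there is one pre-dose SAE rule:

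- In 8.1.1, limit the procedure-related restriction on SAEs to patients who have signed only the molecular pre-screening consent.
- State that, from signature of the main study consent, all SAEs are captured and reported as in 8.2.2, regardless of causality and including screen failures.
- State that only non-serious events between main consent and first dose go to medical history.

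This adds no new policy; it brings 8.1.1 into line with the protocol's own SAE section. In the same edit, check 7.2.2.1, which sends significant new physical findings after consent to the AE page, against the medical-history rule for non-serious pre-dose events.

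The cost is a short wording change and slightly more SAE forms. Under Protocol 12.1 it needs a written amendment with the usual approvals, so it could be carried in the next planned amendment.

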# Unlike routine safety assessments, SAEs are monitored continuously and have special reporting requirements; see Section 8.2.

All adverse events should be treated appropriately. Such treatment may include changes in study drug treatment including possible interruption or discontinuation, starting or stopping concomitant treatments, changes in the frequency or nature of assessments, hospitalization, or any other medically required intervention. If a concomitant medication or non-drug therapy is given, this action should be recorded on the Adverse Event eCRF.

Once an adverse event is detected, it should be followed until its resolution or until it is judged to be permanent, and assessment should be made at each visit (or more frequently, if necessary) of any changes in severity, the suspected relationship to the study treatment, the interventions required to treat it, and the outcome.

Information about common side effects already known about the investigational drug can be found in the Investigator's Brochure or will be communicated between IB updates in the form of Investigator Notifications. This information will be included in the patient informed consent and should be discussed with the patient during the study as needed.

